12.2.1 Analysis of Adverse Events in the Extension Study

Adverse events (AEs) in the extenstion study will be summarized using system organ classes (SOCs) and preferred terms (PTs) from the Medical Dictionary for Regulatory Activities (MedDRA) Version 19.0 or higher by the six analysis groups as described in Section 5.3.

For each AE summary, the number and percentage of subjects experiencing at least one AE will be presented. Subjects reporting more than one AE within a SOC will be counted only once for that SOC. Subjects reporting more than one AE for a PT will be counted only once for that PT.

Treatment-emergent AEs are defined as AEs with a start date on or after the first dose of study drug in the extension study. AEs starting more than 30 days following discontinuation of study drug will not be included in summaries of treatment-emergent

COBVIE Elagolix (ABT-620) M12.816 - Statistics

Elagolix (ABT-620) M12-816 – Statistical Analysis Plan Version 2.0 – 24 May 2018

AEs. Post-Treatment AEs are defined as AEs starting more than 30 days following discontinuation of study drug in the Treatment Period of this study.

When summarizing AEs by relationship or severity, if a subject has an event with unknown severity or relationship then the subject will be counted in the severity/relationship category of "unknown" even if the subject has a second occurrence of the same event with a severity/relationship present. The only exception is if the subject has a second occurrence of the same event with the most extreme severity (i.e., "severe") or the most extreme relationship category (i.e., "reasonable possibility"). In this case, the subject will be counted under these most extreme severity/relationship categories.

Treatment Period

The number and percentage of subjects with treatment-emergent AEs will be calculated by analysis group as follows:

- Any AEs
- Any AEs by primary MedDRA system organ class (SOC) and preferred term (PT)
- Any AEs occurring in ≥ 5% of subjects by primary MedDRA system organ class (SOC) and preferred term (PT)
- Any AEs by PT in descending frequency of 12 month elagolix 300 mg BID plus E2/NETA treatment group
- Any AEs by maximum severity (by primary MedDRA SOC and PT)
- Any AEs by maximum relationship (by primary MedDRA SOC and PT)
- Any AEs reasonably possibly related to study drug (by primary MedDRA SOC and PT, by PT)
- Any AEs leading to study drug discontinuation (by primary MedDRA SOC and PT)
- Any serious AEs (SAEs) (by primary MedDRA SOC and PT, by PT)
- Any severe AEs (by primary MedDRA SOC and PT)

- Any SAEs reasonably possibly related to study drug (by primary MedDRA SOC and PT, by PT)
- Any SAEs leading to study drug discontinuation (by primary MedDRA SOC and PT)
- Any AEs of special interest as specified in Appendix M
- Any AEs leading to death (by primary MedDRA SOC and PT)

A listing by the four main analysis group as in Section 5.3 of treatment-emergent AEs with subject IDs will be generated. Listings of all treatment-emergent SAEs, AEs leading to death, and AEs leading to study drug discontinuation will be generated.

Summary of total number of hot flush and night sweat by subject-reported severity categories, summary of total number of hot flush and night sweat by maximum subject-reported severity, and summary of time to first onset of hot flush and night sweat will be provided. Listings of subjects associated with hot flush and night sweat will also be provided.

Post-Treatment Follow-Up Period

The Post-Treatment AEs will be summarized as follows:

- Any AEs by primary MedDRA SOC and PT
- Any SAEs by primary MedDRA SOC and PT.

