### 6.1.3 Relationship to Study Drug

The investigator will use the following definitions to assess the relationship of the adverse event to the use of study drug:

Reasonable Possibility	An adverse event where there is evidence to suggest a causal relationship between the study drug and the adverse event.
No Reasonable Possibility	An adverse event where there is no evidence to suggest a causal relationship between the study drug and the adverse event.

For causality assessments, events assessed as having a reasonable possibility of being related to the study drug will be considered "associated." Events assessed as having no reasonable possibility of being related to study drug will be considered "not associated." In addition, when the investigator has not reported a causality or deemed it not assessable, AbbVie will consider the event associated.

If an investigator's opinion of no reasonable possibility of being related to study drug is given, an "Other" cause of event must be provided by the investigator for the serious adverse event.

[figure not shown]

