### **8.1.8.2 Adverse Events**

Adverse events (AEs) will be coded using the Medical Dictionary for Regulatory Activities (MedDRA) dictionary. Treatment-emergent adverse events (TEAEs) will be summarized for each treatment group. TEAEs are defined as AEs with a start date on or after the first dose of the study drug and within 30 days of the last dose of the study drug in the Extension Study. AEs starting more than 30 days following discontinuation of the study drug will not be included in the summaries of TEAEs. AEs starting more than 30 days following discontinuation of the study drug will be summarized separately as Post-Treatment AEs.

When summarizing TEAEs by relationship or severity, if a subject has an event with unknown severity or relationship, then the subject will be counted in the severity/relationship category of "unknown," even if the subject has a second occurrence of the same event with a severity/relationship present. The only exception is if the subject has a second occurrence of the same event with the most extreme severity (i.e., "severe") or a relationship category of "reasonable possibility." In this case, the subject will be counted under these most extreme severity/relationship categories.

The frequencies and percentages of subjects with TEAEs will be calculated for each treatment group as follows:

- Any event
- By system organ class, and preferred term
- By system organ class, preferred term and maximum relationship
- By system organ class, preferred term and maximum severity
- Any event and by system organ class and preferred term for events resulting in study drug discontinuation
- Any event and by system organ class and preferred term for serious events
- Any event and preferred term for AESI's (e.g., hypoestrogenic adverse events)

The Post-Treatment AEs will be summarized in a similar manner as the TEAEs described above.

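### Missing or non-assessable causality counts as drug-associated in protocol 6.1.3 but as 'unknown' in protocol 8.1.8.2 and SAP 12.2.1, so the relationship tables can show fewer related subjects than 6.1.3 implies

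*SAP*

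**What the plan says.** Protocol 6.1.3 (Relationship to Study Drug) gives the investigator two causality categories, 'reasonable possibility' and 'no reasonable possibility'. It then maps them to a sponsor classification: "events assessed as having a reasonable possibility of being related to the study drug will be considered" associated, and the others not associated. It also covers the remaining case: "when the investigator has not reported a causality or deemed it not assessable, AbbVie will consider the event associated". It provides no third class.

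Protocol 8.1.8.2 (Adverse Events) does use a third class, named 'unknown', in tables split on either attribute: "if a subject has an event with unknown severity or relationship, then the subject will be counted in the severity/relationship category" so named. This applies even where another occurrence of that event has a stated value.

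SAP 12.2.1 repeats this: "if a subject has an event with unknown severity or relationship then the subject will be counted in the" category 'unknown'. It continues: "The only exception is if the subject has a second occurrence of the same event with the most extreme severity", or with the most extreme relationship, which it identifies as 'reasonable possibility'.

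The treatment-period outputs in SAP 12.2.1 include AEs by maximum relationship, a table headed "Any AEs reasonably possibly related to study drug", and the corresponding table for SAEs. The post-treatment AE tables in the SAP are not split by relationship, so the point does not touch them.

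**The concern.** An event with no usable investigator causality is associated with study drug under one section and of unknown relationship under another. The conflict lies inside the protocol (6.1.3 against 8.1.8.2) and carries over into the SAP. A programmer who follows the SAP literally would leave such an event out of the related-AE and related-SAE tables, although the protocol says that the sponsor regards it as associated.

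Two things are at stake. The sponsor's classification of an individual event and the study report's tables could disagree about the same SAE. In addition, any difference runs towards fewer drug-related events. Every subject in this extension receives active treatment (protocol 5.6.4), so there is no concurrent placebo rate to set beside the AE rates, and the investigator's attribution carries more of the interpretation.

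**Working it through.** The plan states no figure to reproduce; the check is whether the two rules give the same answer.

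**Inputs.** The default for missing causality comes from protocol 6.1.3. The 'unknown' rule and its exception come from protocol 8.1.8.2 and SAP 12.2.1. The number of events with missing or non-assessable causality, and the group sizes, are not given.

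**Step 1: does any text recode first?** Nothing in either document does. The general rules point away from recoding: protocol 8.1.8.1 does not impute missing safety data unless otherwise specified, and SAP 12.1 bases all safety analyses on observed data.

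**Step 2: every causality pattern for one or two occurrences of the same event.** RP = reasonable possibility, NRP = no reasonable possibility, UNK = not reported or not assessable. For relationship, the SAP order is RP over UNK over NRP. Under 6.1.3, UNK is treated as RP.

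| Occurrences | SAP 12.2.1 | Protocol 6.1.3 | Agree on related? |
|---|---|---|---|
| RP | related | related | yes |
| NRP | not related | not related | yes |
| UNK | unknown | related | **no** |
| RP, RP | related | related | yes |
| RP, NRP | related | related | yes |
| RP, UNK | related | related | yes |
| NRP, NRP | not related | not related | yes |
| NRP, UNK | unknown | related | **no** |
| UNK, UNK | unknown | related | **no** |

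The rules differ on 3 of 9 patterns. In all three, 6.1.3 gives related and the SAP does not. No pattern moves the other way.

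**Step 3: size.** In any one table row, a woman classified differently changes the percentage by 100/n, where n is the number in her group. With assumed sizes:

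- n = 50: 100/50 = 2.0 points
- n = 67: 100/67 = 1.5 points
- n = 100: 100/100 = 1.0 point
- n = 200: 100/200 = 0.5 points

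This is a maximum per woman per row. It is zero in a preferred-term row if she also has an RP occurrence of that event. It is zero in the any-AE row if she has any other related AE.

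**Step 4: illustration of an any-AE row (all inputs assumed).** Take a group of 100 women, 30 of whom have a reported related AE. Suppose k further women have missing-causality events and no related one. The SAP rule gives 30/100 = 30.0% throughout. The 6.1.3 rule gives (30 + k)/100, which is 30.0%, 31.0%, 32.0% and 35.0% for k = 0, 1, 2 and 5.

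**The case against.** The strongest reply is that the difference may never occur. Investigators must record the relationship for every AE (protocol 6.1), the principal investigator reviews eCRFs for completeness (protocol 10.2), and discrepant data are clarified before lock (protocol 8.1.3, SAP 4.4). If no causality is missing at lock, the tables are identical. This stands: a reader might infer that the tables will undercount, and the documents do not support that without a count of such events. It does not remove the conflict, because both sections expressly provide for the case, and a query can fill in an unreported causality but need not change a judgement that causality cannot be assessed.

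A second reply is that the rules work in sequence: the sponsor's default is applied first, and the 'unknown' rule then has nothing left to act on for relationship. This is possible in practice, but neither document states it. Equally, 6.1.3 might be meant for safety reporting only, but it sets no such limit.

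Third, SAP 12.2.1 does not say in terms how unknowns enter the two related-event tables. That is true. Exclusion is the natural reading, since a woman counted as 'unknown' is not counted as related and nothing puts her back.

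Fourth, the information is not lost. 'Unknown' is a displayed category that outranks 'no reasonable possibility', and all treatment-emergent SAEs are listed. This stands and limits the harm: the cases are labelled differently, not reported as unrelated.

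Finally, a reader might infer that the study is uncontrolled or that the SAP departs from the protocol's analysis section. Neither holds. Former placebo subjects are randomized 1:1, elagolix alone is the stated reference arm (protocol 5.6.1), and the SAP matches protocol 8.1.8.2. What is missing is a placebo arm, and the inconsistency begins inside the protocol.

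**Conclusion.** The conflict between the stated rules is real, and its direction is fixed. Applied as written, SAP 12.2.1 can lower the related counts relative to protocol 6.1.3 and cannot raise them. The outputs affected are AEs by maximum relationship and the reasonably possibly related AE and SAE tables, with preferred-term rows the most exposed.

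The size is conditional. It requires events with missing or non-assessable causality at lock, in women with no 'reasonable possibility' occurrence of the same event, and is then bounded by 100/n points per woman per row. The number of such events is not given and may be zero. The conclusion assumes that 'unknown' relationship in the analysis rule covers what 6.1.3 calls not reported or not assessable; neither document defines it otherwise. No estimate of related SAEs per group can be drawn from the documents, so no claim is made that a particular SAE row would change.

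**What to change.** Add one sentence to SAP 12.2.1: for all relationship summaries, an AE with missing or non-assessable causality is counted as 'reasonable possibility', in line with protocol 6.1.3. Keep 'unknown' for severity only. Footnote each relationship table with the number of events assigned this way, so that the reported and assigned cases can be told apart. Align protocol 8.1.8.2 at the next amendment; this does not need an amendment of its own. If the sponsor intends 6.1.3 to govern safety reporting only, the SAP should instead say so and justify the different rule for tables.

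The cost is one SAP sentence, a footnote, and a matching edit whenever the protocol is next amended. The downside is that related-event rates may rise slightly. If no causality is missing at lock, no count changes.

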12.3 Laboratory Variables

Hematology, clinical chemistry, urinalysis, and endocrine panel variables collected in this study are specified in the protocol. An overall summary will be provided for all laboratory variables. For all other analysis, analysis will be performed for the following laboratory variables: lipid variables, liver variables (alkaline phosphatase, ALT, AST, bilirubin), glucose, hemoglobin, hematocrit, platelet count, and Red Blood Cell (RBC) count.

For lipid variables, in addition to low-density lipoprotein cholesterol (LDL-C), highdensity lipoprotein cholesterol (HDL-C), total cholesterol, triglycerides (TG), and apolipoprotein A and B, the following ratios will be included: the ratio of total cholesterol to HDL-C, the ratio of LDL-C to HDL-C, the ratio of TG to HDL-C, and the ratio of non-HDL-C (calculated as total cholesterol minus HDL-C) to HDL-C.

12.3.1 Analysis of Laboratory Variables

Treatment Period

All laboratory variables will be summarized with mean, median, standard deviation, minimum, and maximum by the four main analysis groups as in Section 5.3.

For continuous laboratory variables, the analyses of change (for all laboratory variables of interest) and percent change (only for lipid variables) from Baseline to each relevant visit in the Treatment Period will be summarized by the four main analysis groups as in Section 5.3.

In the Treatment Period, the laboratory data will be categorized as low, normal, or high based on the normal ranges of the laboratory used in this study. The low or high laboratory values will be flagged in the data listings.

In the Treatment Period, shift tables for change from Baseline according to the normal range will be provided for laboratory parameters of interest mentioned above by the six analysis groups as in Section 5.3. The shift tables will tabulate the number and percentage of subjects with baseline values of high or normal to post-baseline low, baseline values of low or normal to post-baseline high, baseline values of high or normal to final post-baseline low, baseline values of low or normal to final post-baseline high. The final value in the Treatment Period refers to the last non-missing value collected within 3 days following the last dose of study drug.

In the Treatment Period, shift tables for change from Baseline to the minimum, maximum, and final value will also be presented based on the Common Terminology Criteria for

Adverse Events (CTCAE) v 4.0 grades⁵ for the laboratory tests. For those analytes that are not reflected in the CTCAE, Exceptions to Standard CTCAE Lab Grading Criteria for Elagolix Studies will be used as specified in Appendix N. The final value in the Treatment Period is as defined above. The number and percentage of subjects meeting the CTCAE will be summarized by the four main analysis groups as in Section 5.3 in the Treatment Period.

The number and percentage of subjects meeting the following criteria will be summarized at Baseline and each relevant visit by the six analysis groups as in Section 5.3 in the Treatment Period:

- Total cholesterol: $\leq 300, > 300 \leq 400, > 400 \leq 500$, and > 500 mg/dL
- HDL-C: < 40 and ≥ 40 mg/dL
- LDL-C: $< 130, \ge 130 < 160, \ge 160 < 190, \text{ and } \ge 190 \text{ mg/dL}$
- TG: ≤ 150 , $> 150 \leq 300$, $> 300 \leq 500$, $> 500 \leq 1000$, and > 1000 mg/dL
- LDL-C/HDL-C ratio: ≤ 3 , and > 3
- Total cholesterol/HDL-C ratio: ≤ 4.5 , and > 4.5.

In addition, the number and percentage of subjects who have potentially clinically significant (PCS) lipid values meeting the following criteria any time during the Treatment Period will be summarized by the six analysis groups as in Section 5.3:

- Total cholesterol > 200 mg/dL
- LDL-C > 130 mg/dL
- LDL-C > 160 mg/dL
- HDL-C < 40 mg/dL
- TG > 150 mg/dL
- TG/HDL-C ratio > 3.5
- LDL-C/HDL-C ratio > 4.

Plots will be provided by the four main analysis groups as in Section 5.3 for HDL-C, LDL-C, triglycerides, and hemoglobin during the Treatment Period:

- Final post-baseline lab values vs. Baseline lab values;
- Final post-baseline lab values vs. Baseline lab values for subjects with NCI CTCAE Grade 3 or 4;
- Maximum post-baseline lab values vs. Baseline lab values;
- Maximum post-baseline lab values vs. Baseline lab values for subjects with NCI CTCAE Grade 3 or 4.

Plots will be provided by the four main analysis groups as in Section 5.3 for HDL-C, LDL-C, and triglycerides during the Treatment Period:

• Mean percent change from Baseline in lipid over month.

Post-Treatment Follow-Up Period

All laboratory variables will be summarized with mean, median, standard deviation, minimum, and maximum by the four main analysis groups as in Section 5.3.

Laboratory data collected more than 3 days after the last dose of study drug in the Treatment Period will be included in the summary of data from the Post-Treatment Follow-up Period. Baseline for summaries/analyses in the Post-Treatment Follow-up Period is the same as Baseline for summaries/analyses in the Treatment Period.

In the Post-Treatment Follow-up Period, the following summaries will be presented:

- During the Post-Treatment Follow-up Period, shift tables for change from Baseline to relevant Post-Treatment Follow-up visit(s) according to the normal ranges will be provided for LDL-C, HDL-C, TG, and total cholesterol by the six analysis groups as in Section 5.3.
- During the Post-Treatment Follow-up Period, shift tables for change from Baseline to relevant Post-Treatment Follow-up visit(s) will also be presented

based on the CTCAE grades for LDL-C, HDL-C, TG, and total cholesterol by the four main analysis groups as in Section 5.3.

• Change in liver enzymes (SGPT/ALT, SGOT/AST, total bilirubin, and alkaline phosphatase) and lipid parameters (LDL-C, HDL-C, TG, and total cholesterol) from Baseline to relevant Post-Treatment Follow-up visit(s) will be summarized by the four main analysis groups as in Section 5.3 with descriptive statistics.

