12.5 Vital Signs and Body Weight

Vital sign variables include pulse rate, sitting systolic blood pressure, sitting diastolic blood pressure, and oral body temperature.

Vital sign variables will be summarized with mean, median, standard deviation, minimum, and maximum by the four main groups as in Section 5.3.

Analyses of mean change from Baseline to each relevant visit during the Treatment Period in vital sign variables and weight will be performed by the four main groups as in Section 5.3.

The number and percentage of subjects who have PCS vital sign and weight values meeting the following criteria will be summarized by the six analysis groups as in Section 5.3. All increase/decrease is calculated from Baseline to a post-baseline visit in the Treatment Period.

The number and percentage of subjects who have a sustained PCS vital sign value and a listing of these subjects will be provided. A sustained PCS value is defined as 3 consecutive PCS values in the Treatment Period.

- Diastolic blood pressure
 - $\circ \leq 50 \text{ mmHg and} \geq 15 \text{ mmHg decrease}$
 - \circ > 90 mmHg and \geq 15 mmHg increase
 - $\circ \geq 100 \text{ mmHg}$
- Systolic blood pressure
 - $\circ \leq 90 \text{ mmHg and} \geq 20 \text{ mmHg decrease}$
 - $\circ \geq 140 \text{ mmHg and} \geq 20 \text{ mmHg increase}$
 - $\circ \geq 160 \text{ mmHg}$
- Pulse rate
 - $\circ \leq 45$ bpm and ≥ 15 bpm decrease
 - \circ > 100 bpm and \geq 15 bpm increase
 - $\circ \geq 120 \text{ bpm}$
- Weight
 - $\circ ~~ \geq 5\%~decrease$
 - $\circ \geq 7\%$ increase.

CODVIE Elagolix (ABT-620) M12-816 - Statistics

Elagolix (ABT-620) M12-816 – Statistical Analysis Plan Version 2.0 – 24 May 2018

Change in vital signs from Baseline to relevant Post-Treatment Follow-up visit(s) (Post-Treatment Month 1, Month 3, Month 6, Month 9, Month 12, and Final Visit) will be summarized by the four main groups as in Section 5.3 with descriptive statistics.

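### The any-time counts of potentially clinically significant lipid values in SAP 12.3.1 ignore baseline, and three of the seven limits have no baseline count to set beside them

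*SAP*

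**What the plan says.** SAP Section 12.3.1 plans, among other laboratory summaries, "the number and percentage of subjects who have potentially clinically significant (PCS) lipid values meeting the following criteria any time during the Treatment Period". There are seven criteria: "Total cholesterol > 200 mg/dL", "LDL-C > 130 mg/dL", LDL-C above 160 mg/dL, HDL-C below 40 mg/dL, triglycerides (TG) above 150 mg/dL, "TG/HDL-C ratio > 3.5" and "LDL-C/HDL-C ratio > 4". Results are shown for all six analysis groups. Nothing excludes women by baseline status or stratifies on it.

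Just before this, the same section plans a banded lipid table: "The number and percentage of subjects meeting the following criteria will be summarized at Baseline and each relevant visit". Its cut-points are:

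- total cholesterol 300, 400 and 500 mg/dL
- HDL-C 40 mg/dL
- LDL-C 130, 160 and 190 mg/dL
- TG 150, 300, 500 and 1000 mg/dL
- LDL-C/HDL-C 3
- total cholesterol/HDL-C 4.5

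Section 12.3.1 also plans normal-range shift tables from baseline, CTCAE-grade shift tables to the minimum, maximum and final value, and change and percent change from baseline for lipids.

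Elsewhere the SAP is explicit about baseline. For vital signs and weight (Section 12.5) it says "All increase/decrease is calculated from Baseline to a post-baseline visit in the Treatment Period". Six of the nine blood-pressure and pulse criteria there, and both weight criteria, require a change from baseline. A sustained abnormality is defined as three consecutive abnormal values. For liver tests (Section 12.3.2) the SAP states that the baseline value is disregarded. For lipids it is silent.

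**The concern.** A rate labelled potentially clinically significant and on treatment will be read as something that happened on treatment. As defined, it mixes three groups: women who were over the limit beforehand, women whose lipids rose, and women near the limit who cross it by ordinary visit-to-visit variation. For example, a woman with total cholesterol of 215 mg/dL at baseline and 210 on treatment counts as a case although her value fell.

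The lipid question matters in this programme. Protocol Section 3.2.2 lists changes in serum lipids among the adverse events of special interest and reports increases on elagolix in the Phase 2 fibroid studies. SAP Appendix M lists lipid abnormalities. Protocol Section 3.5 cites attenuation of lipid increases by E2/NETA as part of the benefit-risk case. Under Protocol Section 5.6.4 all women take active drug, so no untreated group shows the background rate.

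**Working it through.** **Step 1. Match each limit to the table that includes Baseline (SAP 12.3.1).**

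| PCS limit | Cut-point at Baseline | Match |
|---|---|---|
| Total cholesterol > 200 | lowest cut 300 | none |
| LDL-C > 130 | bands start at ≥ 130 | except at the boundary |
| LDL-C > 160 | band starts at ≥ 160 | except at the boundary |
| HDL-C < 40 | < 40 / ≥ 40 | exact |
| TG > 150 | ≤ 150 / > 150 | exact |
| TG/HDL-C > 3.5 | ratio not in the table | none |
| LDL-C/HDL-C > 4 | only cut is 3 | none |

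Three of seven limits have no baseline count, two have one that differs at the boundary, and two match exactly.

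**Step 2. Can another planned summary supply the three missing counts?** Normal-range shift tables use the laboratory's ranges. The documents do not give these, so they cannot be assumed to equal 200, 3.5 or 4, and the SAP does not say whether the ratios have normal ranges. Means and mean changes do not give a count at a limit. The plots of maximum against baseline cover HDL-C, LDL-C and TG among the lipids, but not total cholesterol or the ratios. So the answer is no.

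**Step 3. Count the chances to cross.** Protocol Appendix C schedules the lipid panel at Months 1 to 6. That gives up to six scheduled on-treatment values against one baseline value.

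**Step 4. Illustrate the size with no drug effect.** The documents give no lipid means, SDs or correlations, so these inputs are assumptions shown as a range. Let p be the share over the limit at baseline and r the within-woman correlation. Each value is √r·(woman's level) + √(1−r)·(visit error), both standard normal. A value is over the limit if it exceeds z(1−p). One baseline and six on-treatment values were simulated for 1,000,000 women per setting.

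| p | r | Counted at any of six visits | Of those, already over at baseline | Rate among women not over at baseline |
|---|---|---|---|---|
| 10% | 0.6 | 29.0% | 27.5% | 23.4% |
| 10% | 0.9 | 18.2% | 51.1% | 9.9% |
| 30% | 0.6 | 62.3% | 44.4% | 49.5% |
| 30% | 0.9 | 44.9% | 64.5% | 22.8% |
| 50% | 0.6 | 82.0% | 58.9% | 67.5% |
| 50% | 0.9 | 66.0% | 74.2% | 34.1% |

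Consistency check for p = 30%, r = 0.6. Already over and counted: 0.623 × 0.444 = 0.277. Not over and counted: 0.70 × 0.495 = 0.347. The sum is 0.624, which agrees with 0.623 within rounding. Of the 30% over at baseline, 0.277/0.30 = 92% are counted again. At r = 0.9 this is 0.449 × 0.645/0.30 = 97%.

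**Step 5. A second illustration, for total cholesterol > 200 only.** Assume a mean of 180 to 200 mg/dL, between-woman SD 35, within-woman SD 10 to 15 and no drug effect. Then 29% to 50% are over at baseline, 42% to 70% are counted, and 59% to 77% of those counted were already over. The implied correlations are 35²/(35²+15²) = 0.84 and 35²/(35²+10²) = 0.92, so these results fit the table above.

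**The case against.** The strongest reply is that this table was never meant to carry the lipid conclusion. It is introduced as an addition and is untested, since SAP Section 12.1 confines safety testing to BMD. Change from baseline is analysed in several other ways. The normal-range shift tables count women going from low or normal to high, so a woman already high cannot appear as a new high. The CTCAE shift tables run from baseline to the worst value, and Appendix N grades LDL-C at 130, 160 and 190 mg/dL and flags HDL-C below 40, so those limits are largely covered. Baseline-free counts are also an ordinary choice in this SAP: the liver criteria and three of the nine blood-pressure and pulse criteria work the same way. All of this stands, and it limits the point to one table.

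A reader might go further and infer two things that the documents do not support.

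- **That no baseline lipid figure is planned.** SAP Section 12.1 requires baseline means at each visit, and four of the seven limits have a baseline count, two of them differing only at the boundary. What is missing is a count at three cut-points.
- **That attenuation by E2/NETA cannot be read from these rates.** Former placebo women are randomised 1:1 to the two regimens (Protocol Section 5.5.1), with baseline re-set before their first active dose (SAP Section 7.1). Prior abnormality and visit noise are balanced between these two groups in expectation, so their rates can be compared descriptively. That argument does not extend in the same way to the continuing groups, which were not re-randomised and entered after completing a pivotal study and meeting BMD criteria. It also does not help the two pooled groups, which combine both regimens.

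The simulations assume no drug effect. They therefore cannot show what the observed rates will mostly reflect.

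**Conclusion.** The point holds as a limited reporting gap. The PCS lipid rates include women over a limit before treatment. For three of seven limits the number already over cannot be seen, and for two more the definitions differ at the boundary. Taken alone, the rates cannot separate pre-existing from on-treatment abnormality or speak to elagolix against no treatment. No table in an all-active extension could make that second comparison.

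The reading that baseline is ignored rests on the absence of any restriction, not on an explicit statement. The size for this trial is unknown. Under the assumptions shown, the share of counted women who were already over ranges from about 28% (10% over at baseline, correlation 0.6) to 74% (50%, 0.9). These figures are illustrations, not estimates for this trial. The lipid conclusion does not depend on this table, so this is a worthwhile low-cost improvement and not a flaw in the safety evaluation.

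**What to change.** In SAP Section 12.3.1:

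1. Keep the any-time count, so that women already over a limit stay visible.
2. Beside it, for all seven limits, show the number meeting the limit at Baseline, and the rate among women not meeting it at Baseline.
3. Name the Section 7.1 baseline in each column: re-set before the first active dose for former placebo women, and the pivotal-study baseline for continuing women.
4. Use the same inequality for LDL-C 130 and 160 mg/dL in both tables.
5. Add a sustained version over consecutive visits, as Section 12.5 does for vital signs. The restricted denominator alone is not enough: with no drug effect, 10% to 23% (10% over at baseline) or 23% to 50% (30% over) of women not over at baseline still cross at least once in six visits.

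No new data are needed. The cost is SAP wording, one larger table and smaller denominators that differ by criterion.
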